#### 9.3.2.2. Mepolizumab Drug Product 2 Period

The mepolizumab drug product 2 period is defined as being from the date and time of the first administration of MDP2 to the day of the last administration using MDP2 + another 28 days (but no greater than the data collection cut-off date).

i.e. time within the mepolizumab drug product 2 period will be defined as:

(Date of last MDP2 administration) – (Date of first MDP2 administration) + 28  
(but no greater than the data collection cut-off date)

## 9.4. Values of Potential Clinical Importance

Haematological and clinical chemistry data from subjects who have values outside the normal range and values of potential clinical concern will be listed. Graphical displays of liver function test results will be produced as described in Section 12.9 to identify any liver function tests results which may be of clinical concern. See attachment: Section 18.3 for reference values of potential clinical concern.

## 9.5. Adverse Events

Adverse events will be coded using the Medical Dictionary for Regulatory Activities (MedDRA) coding dictionary. Classification of an AE as pre-, on- or post-treatment will be made with reference to the study treatment start and stop dates and the AE onset date. If the AE onset date is missing or partial then the AE will be considered on-treatment unless there is evidence to the contrary (e.g. the month of the onset date is present and is less than the month of the first dose of study medication). AEs with onset up to 4 weeks after the last dose of treatment will be considered on-treatment. AEs with onset after this period will be considered post-treatment but will be assigned to the treatment previously received.

Any SAEs for screen failures or run-in failures will be classified as pre-treatment SAEs.

The most frequent on-treatment AEs will be defined as AEs with frequency  $\geq 3\%$  (prior to rounding).

When presenting summaries of adverse events by drug product, the onset date and time of each event will be used to deem in which drug product period the event occurred. For the definitions of the two drug product periods, see Section 9.3.2.1 and Section 9.3.2.2. When presenting the data in this way, if the AE onset date or time is missing or partial then the most conservative approach possible will be taken.

### 9.5.1. Exposure Adjusted Adverse Events

The number of events per 1000 subject-years of exposure will be calculated as:

$$\frac{1000 * \text{Number of Adverse Events}}{(\text{Total Duration of Exposure in Days}) / 365.25}$$

## 10. STUDY POPULATION

### 10.1. Disposition of Subjects

A summary of the number of subjects included in each population will be produced.

The proportion of screen failures, the proportion who reported each reason for screen failure, the proportion of run-in failures and the proportion who reported each reason for run-in failure will be presented for the ASE population.

The proportion of subjects in the AT population who has withdrawn from the study, and reported each reason for withdrawal, will be presented. A Kaplan-Meier plot showing the percentage of subjects withdrawing from the study over time will be produced for the AT Population.

The proportion of subjects in the AT population at each centre and within each country and region will be presented. Subject number in MEA115666, treatment received in MEA115666, subject number in MEA112997 and treatment assigned in MEA112997 and will be listed for each centre in the AT population.

## **10.2. Protocol Deviations**

The proportion of subjects in the AT population who failed each inclusion, exclusion or Visit 2 criterion will be presented. Protocol deviations will be summarised and listed for the AT Population.

## **10.3. Demographic and Baseline Characteristics**

### **10.3.1. Demography and Race**

Demographic characteristics (age, sex, ethnicity, height, weight and body mass index) will be summarised and listed.

The proportion of subjects reporting each race and racial combination and each detailed race and racial combination will be presented. Race will be listed.

### **10.3.2. Medical Conditions**

An update in each subject's medical history since completing the medical history form in the MEA112997 trial will be collected at Visit 1 (Screening). If a subject reports no change in medical history, the respective subject's medical history information will be copied over from the MEA112997 trial.

The proportion of subjects who report medical conditions in each medical condition class will be presented, for past and current conditions separately. Past and current medical conditions will be listed.

### **10.3.3. Cardiovascular Assessment**

A summary of the baseline cardiovascular assessment will be presented. The proportion of subjects who report a family history of medical conditions that may indicate predisposition towards cardiovascular conditions will be summarised.

### **10.3.4. Since Completion of MEA112997**

The number of days and number of exacerbations experienced between the completion of MEA112997 and Visit 1 (Screening) in MEA115666 will be summarised. The completion date of MEA112997 will be considered as the Visit 16 (Week 52) date for

those subjects who completed the study, and will be considered as the date of withdrawal for those subjects that withdrew from the trial prematurely.

### **10.3.5. Baseline Lung Function Tests**

The following Baseline (Visit 2) clinic lung function results will be summarised:

- Pre bronchodilator FEV1 (mL)
- Pre bronchodilator percent predicted FEV1 (%)
- Pre bronchodilator Forced Vital Capacity FVC (mL)
- Pre bronchodilator FEV1/FVC

### **10.4. Treatment Compliance**

A summary of treatment compliance is not applicable to this study; however number of treatments received is summarised in the Extent of Exposure Section [12.1](#).

### **10.5. Concomitant Medications**

The proportion of subjects reporting each concomitant medication will be presented. Multi-ingredient medications will be presented according to their combination ATC classification rather than the classifications of the ingredients. Summaries will be split into asthma and non-asthma concomitant medications, as well as into those taken pre-treatment, during treatment and post-treatment (as described in Section [9.3](#)). Asthma medication outputs will not display the ATC grouping.

Classification of a medication as pre-, on- or post-treatment will be made with reference to the study treatment start and stop dates and the medication start date. If the medication start date is missing or partial then the medication will be considered on-treatment unless there is evidence to the contrary (e.g. the month of the start date is present and is less than the month of the first dose of study medication). Medications with a start date of up to 4 weeks after the last dose of treatment will be considered on-treatment. Medications with a start date after this period will be considered post-treatment.

Pre- and on-treatment respiratory medications will be summarised separately.

A medication will be summarised in every period (pre/during/post) in which it was taken, so a medication that was started in the run-in and stopped during active treatment will appear in both the pre-treatment and the during treatment tables.

A listing of the relationship between ATC level 1, ingredient and verbatim term will be produced together with listings of all asthma and non-asthma concomitant medications.

## **11. EFFICACY ANALYSES**

Efficacy data will be summarised using appropriate measures (means/geometric means, standard deviations, medians and ranges for continuous variables and frequencies and

percentages for categorical variables). Unless otherwise stated, analyses will be conducted only for the AT Population.

### **11.1. Annualised Rate of Exacerbations**

The frequency of exacerbations of asthma collected during the on-treatment phase (See Section 9.3.1) will be summarised for the AT population. For consistency, exacerbations separated by less than 7 days will be treated as a continuation of the same exacerbation (See Section 9.2.2).

The annualised rate of exacerbations will be estimated using a negative binomial generalised linear model with a log link-function. The covariates listed in Section 8.2 will be used in the model. The estimated mean rate per year and 95% confidence interval will be presented. (The estimates of the mean rates should be presented using the observed marginals of the sample covariates).

The annualised rate of exacerbations will also be estimated according to blood eosinophil level of  $\geq 150/\mu\text{L}$  or  $< 150/\mu\text{L}$  at baseline within MEA115666.

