### 8.2. Other Strata and Covariates

A covariate for region as described above will be included in all model-based analyses. Terms for baseline disease severity (as baseline % predicted pre-bronchodilator FEV1), the annualised rate of exacerbations in the interval between the MEA112997 trial and the screening visit of this study (as an ordinal variable: 0.0-<1.0, 1.0-<2.0, 2.0-<3.0, 3.0-<4.0, ≥4, See Section 9.2.3) and time on-treatment (as an offset variable) will also be included when estimating the annualised rate of exacerbations.

If there are insufficient subjects in each region or exacerbation rate category for the statistical procedures to converge satisfactorily, further combining of these covariates will be considered.

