### 9.2.3. Annualised Rate of Exacerbations in the Interval Between Studies

The annualised rate of exacerbations in the gap between the MEA112997 trial and the screening visit of this study will be calculated as:

For those subjects that completed the study:

$$\frac{\text{Total Number of Exacerbations Since the Completion of MEA112997}}{((\text{Date of Screening MEA115666}) - (\text{Visit 16 (Week 52) date}))/365.25}$$

For those subjects that withdrew from the trial early:

$$\frac{\text{Total Number of Exacerbations Since the Completion of MEA112997}}{((\text{Date of Screening MEA115666}) - (\text{Date of withdrawal}))/365.25}$$

This rate will be derived and then categorised as explained in Section 8.2. A value of 365.25 represents the average number of days in a year.

It should be noted that the number of exacerbations reported between the completion of MEA112997 and screening of MEA115666 is self-reported and not subject to verification.

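### The rule for presenting the annualised exacerbation rate does not state the averaging scale, and its usual reading under a log link gives a rate below the population mean rate.

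*SAP*

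**What the plan says.** SAP 11.1 states: "The annualised rate of exacerbations will be estimated using a negative binomial generalised linear model with a log link-function". On the output it says "The estimated mean rate per year and 95% confidence interval will be presented", followed by the presentation rule: "The estimates of the mean rates should be presented using the observed marginals of the sample covariates".

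The covariates are in SAP 8.2. For region: "A covariate for region as described above will be included in all model-based analyses". Baseline percent predicted pre-bronchodilator FEV1 enters as the severity term. The exacerbation rate between the two studies enters "as an ordinal variable: 0.0-<1.0, 1.0-<2.0, 2.0-<3.0, 3.0-<4.0, ≥4". Follow-up is handled through an offset: "time on-treatment (as an offset variable) will also be included when estimating the annualised rate of exacerbations".

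The results go to Table 6.03 and, by baseline blood eosinophils (below 150/µL, or 150/µL and above), to Table 6.04. SAP 8 names SAS Version 9 or later but no procedure or option. Neither SAP 11.1 nor the table titles say on which scale the averaging is done.

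**The concern.** With a log link, averaging and exponentiating do not commute. Marginals are the separate distributions of the covariates: region proportions, mean FEV1 and history-category proportions. Evaluating the linear predictor there and back-transforming needs only those marginals and is what observed-margins least-squares means ordinarily do. Under that reading the figure labelled as a mean rate is the geometric mean of the subjects' expected rates.

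In a two-arm trial the shift would cancel in the rate ratio. SAP 2.3 and 7 rule out a treatment comparison because there is one arm, so the absolute rate is itself the result. The shift always goes in the favourable direction, and it enters each eosinophil stratum by an amount that depends on the covariate spread in that stratum.

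**Working it through.** **No figure to reproduce.** The documents give no rate, coefficient or dispersion for this endpoint. Protocol 4.1 gives only an upper bound of 608 subjects. Everything below other than the model form and the 608 is assumed.

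**Two readings.** Let x be a subject's covariates and b the fitted coefficients, with the offset set to one year.

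- A, log scale: exp(mean(x)′b).
- B, rate scale: mean(exp(x′b)).

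By Jensen's inequality A ≤ B. If x′b is roughly normal with SD s, A/B = exp(−s²/2): 0.980 at s = 0.2, 0.923 at 0.4, 0.835 at 0.6, 0.726 at 0.8.

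**Exact calculation on five history categories.** Assumed shares are 35/25/18/12/10%, with log-rate step g per category. The mean category index is 0.25 + 2(0.18) + 3(0.12) + 4(0.10) = 1.37.

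For g = 0.3 (rate ratio 1.35 per step):

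- A is proportional to exp(0.3 × 1.37) = 1.508.
- B is proportional to 0.35 + 0.25(1.350) + 0.18(1.822) + 0.12(2.460) + 0.10(3.320) = 1.643.
- A/B = 0.918.

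The same calculation gives 0.991, 0.963, 0.857 and 0.785 at rate ratios of 1.11, 1.22, 1.49 and 1.65 per step.

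**Simulation with all three covariates.** Assumptions: true mean rate 0.70 per year; dispersion 0.8, treated as known; follow-up uniform over 1–4 years and unrelated to risk; history shares as above; region log effects 0, 0, −0.3, 0.2, 0.1 at shares 10/35/25/15/15%; FEV1 effect −0.1 per SD; 500 replicates per setting. Reading A, with a Wald 95% interval, gave:

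| History rate ratio per step | SD of x′b | N=608: estimate (shift), coverage | N=300: estimate (shift), coverage |
|---|---|---|---|
| no covariate effects at all | 0 | 0.692 (−1.1%), 91% | 0.685 (−2.1%), 91% |
| 1.00 | 0.20 | 0.680 (−2.9%), 89% | 0.673 (−3.9%), 92% |
| 1.22 | 0.33 | 0.654 (−6.6%), 69% | 0.651 (−7.1%), 80% |
| 1.35 | 0.45 | 0.625 (−10.7%), 37% | 0.616 (−12.0%), 56% |
| 1.49 | 0.57 | 0.583 (−16.8%), 7% | 0.573 (−18.1%), 26% |
| 1.65 | 0.69 | 0.533 (−23.8%), 0.2% | 0.527 (−24.7%), 5% |

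The 1–2% shortfall in the top row is estimation noise in the fitted coefficients. Reading B, with a delta-method interval that includes covariate sampling, gave 0.695–0.703 with 93–97% coverage in every setting.

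**Second simulation.** With N = 350, a true rate of 0.80 and history as the only covariate, reading A gave 0.772, 0.729 and 0.676 (−3.5%, −8.9%, −15.5%), with coverage of 89%, 63% and 23%, at rate ratios of 1.2, 1.35 and 1.5 per step. Reading B gave 0.796–0.802.

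**Would dropping the covariates do instead?** Take the g = 0.3 example with a true rate of 0.80 and halve follow-up in the highest category.

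- Relative events: 1.643 − 0.5 × 0.10 × 3.320 = 1.477.
- Relative time: 1 − 0.5 × 0.10 = 0.95.
- Crude rate: 0.80 × (1.477/0.95)/1.643 = 0.757.
- Reading A, for comparison: 0.80 × 0.918 = 0.734.

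Two simulations at this rate ratio, with shorter follow-up in high-rate subjects, gave 0.730 and 0.753 for the crude rate and 0.762 and 0.770 for an intercept-only negative binomial model. In the first of these, rate-scale averaging gave 0.800.

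**The case against.** The strongest reply is that the SAP does not prescribe the log-scale calculation. It names no procedure or option, and since it promises a mean rate, the sentence could be read as averaging predicted rates over the sample, which is unbiased for the mean. This stands: the defect is an unspecified scale whose usual reading is biased. A reader might infer that the planned interval will miss the true rate. The documents do not support that, because coverage was close to 90% when the covariates were weak and no gradient is given.

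The log-scale value is also a legitimate quantity, the rate at an average covariate profile. That stands too. It is wrong only under the label of a mean rate.

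The endpoint is one of several secondary ones; the primary endpoint is adverse events. There is no hypothesis, so no error rate depends on it. SAP 11.1 also summarises exacerbation frequency separately. All of this limits the severity. It does not remove the problem, because neither SAP 11.1 nor the table titles name a crude rate or a sample-averaged rate that would reveal the gap.

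A reader might also infer that setting Table 5.22 (rate between the studies) beside Table 6.03 would overstate a fall on treatment. The documents do not support that either. Only the title of Table 5.22 is given, and SAP 9.2.3 says "This rate will be derived and then categorised as explained in Section 8.2", so the table may show frequencies. SAP 7 does not list a before-and-after contrast among its comparisons of interest, and SAP 9.2.3 warns that the earlier counts are self-reported and unverified.

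**Conclusion.** The point holds as a specification gap with a likely downward bias. On the usual reading, Tables 6.03 and 6.04 would report a geometric-type mean under the label of a mean annual rate. Under the assumed values the shift is about 1–4% if the covariates are weak and about 15–25% if exacerbation history has a strong gradient, with coverage running from about 90% to near zero. The true size cannot be derived from the documents. One covariate is the subject's own exacerbation rate, from under 1 to 4 or more per year, so a weak gradient should not be taken for granted.

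A tempting further step is to drop the covariates because there is no arm to compare. The documents argue against it. The study closes country by country (Protocol 3.1) and subjects may be withdrawn for lack of efficacy (Protocol 4.5), so follow-up may depend on region and severity. An intercept-only model is then biased, as the last check shows.

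**What to change.** In SAP 11.1 and the specifications for Tables 6.03 and 6.04:

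- Keep the negative binomial model, its covariates and the offset.
- State that the mean rate is obtained by predicting each subject's annual rate and averaging the predictions on the rate scale over the As Treated sample, and within each eosinophil stratum for Table 6.04.
- Give a delta-method or bootstrap 95% confidence interval for that average.
- Show crude events per person-year beside it as a descriptive check, noting that the two can differ when follow-up depends on risk.
- If the covariate-mean version is also kept, label it as the rate at the average covariate profile.

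The cost is a sentence or two in the SAP and a few lines of code. The reported rate may come out somewhat higher.

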### **11.2. Time to First Exacerbation**

Summaries and graphs of the Kaplan-Meier estimates of the proportion of subjects with an exacerbation over time will be produced.

### **11.3. Asthma Control Questionnaire Score**

Asthma Control Questionnaire (ACQ) score (absolute value and changes from baseline) will be summarised by visit.

### **11.4. FEV1 Measured by Clinic Spirometry**

Pre-bronchodilator FEV1 (absolute value and changes from baseline (mL)) will be summarised by visit.

### **11.5. Blood Eosinophils**

Blood eosinophil count and ratio to baseline will be summarised by visit. Blood eosinophil count and ratio to baseline will be also be summarised by drug product and visit in a separate table. For the definitions of the two drug product periods, see Section 9.3.2.1 and Section 9.3.2.2.

Blood eosinophil counts collected whilst receiving the two drug products will be further compared by summarising the last sample to be collected prior to the first dose of MDP2 and the first sample collected following the first dose with MDP2. This particular table will only include those subjects that have a blood eosinophil sample collected from both drug product periods.

Values of zero cells will be imputed as 0.005 prior to log transformation. Blood eosinophil data will also be listed.

## 12. SAFETY ANALYSES

All safety summaries and listings will be produced for the AT population, with the exception of the table of pre-treatment SAEs and relationship between system organ class, preferred term and verbatim term which will be reported for the ASE population. Similarly, listings of subject numbers for individual AEs, all AEs, fatal AEs and non-fatal SAEs will be reported for the ASE population.

### 12.1. Extent of Exposure

The number of treatments administered and the number of days on-treatment will be summarised and listed. The listing of exposure will also contain information of the drug product administered at each dosing visit. For definition of on-treatment, see Section 9.3.2.

The number of treatments administered and the number of days on-treatment will also be summarised by drug product. For the definitions of the two drug product periods, see Section 9.3.2.1 and Section 9.3.2.2.

### 12.2. Adverse Events

Adverse events will be summarised by preferred term. Numbers will be presented for the whole population. Additionally, events experienced during the first 6 months of treatment within MEA115666 will be presented by treatment assigned within MEA112997.

AEs occurring during pre-treatment, on-treatment and post-treatment phase will be summarised separately.

The number and percentage of subjects experiencing at least one AE of any type, AEs within each body system and AEs within each preferred term will be summarised.

All AEs and SAEs will be summarised by drug product. For the definitions of the two drug product periods, see Section 9.3.2.1 and Section 9.3.2.2.

Exposure adjusted rates of AEs will be presented by drug product to account for any differences in the length of exposure to the two different drug products within the trial. For the definition of exposure adjusted AEs, see Section 9.5.1.

The following summary tables will be produced:

- Overview of all Adverse Events
- Summary of all Adverse Events (on-treatment and post-treatment)
- Summary of drug related Adverse Events (on-treatment)
- Relationship of all Adverse Event SOCs, PTs, and Verbatim Text
- Summary of Most Frequent ( $\geq 3\%$  Incidence prior to rounding) Adverse Events (on-treatment)

- Summary of Number of Subjects and Occurrences of Common On-Treatment Non-Serious Adverse Events by System Organ Class
- Summary of all Adverse Events Experienced During the First 6 Months of Treatment by Treatment Assigned within MEA112997 (on-treatment)
- Summary of all AEs by drug product (on-treatment)
- Summary of Exposure Adjusted AEs by drug product
- Summary of On-Treatment Adverse Events by Highest Anti Drug Antibody Result At Any Time Post Baseline (See Section 12.12 for further details about Immunogenicity)

The following listings will be produced:

- Listing of Subject Numbers for Individual Adverse Events
- Listing of all Adverse Events

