4.5. Withdrawal Criteria

Subjects may be withdrawn from study treatment at anytime by the Investigator if it is considered to be detrimental for them to continue in the study. Reasons for withdrawal can include: an adverse event, lost to follow-up, protocol violation, lack of efficacy, sponsor terminated study, non-compliance, pregnancy, abnormal liver function test, abnormal laboratory results, or for any other reason. Liver chemistry stopping criteria are detailed in Section 6.3.2. In addition, QTc discontinuation criteria are listed below:

- QTc(F)>500 msec or uncorrected QT>600 msec
- Bundle branch block: QTc(F)>530 msec (**Note:** QTc(F)>500 msec for Korean subjects)
- Change from baseline: QTc > 60msec

[Based on average QTc(F) value of triplicate ECGs. If an ECG demonstrates a prolonged QT interval, obtain 2 more ECGs over a brief period, and then use the averaged QTc(F) values of the 3 ECGs to determine whether the patients should be discontinued from the study].

Subjects are free to discontinue participation in the study at anytime. Every effort should be made to have the subject return for a Follow-up visit 4 weeks post last mepolizumab injection. In those instances where the subject specifies the reason for withdrawal of consent, this information will be captured in the eCRF.

A subject should only be designated as lost to follow-up if the site is unable to establish contact with the subject after 3 documented attempts via 2 different methods (phone, text, e-mail, certified letter, etc). These efforts should be documented in the clinic notes at the site.

Subjects may also be withdrawn from this study if mepolizumab becomes commercially available in the respective country, marketing of mepolizumab is no longer being sought in the respective country, or upon decision of the sponsor to discontinue further development of mepolizumab.

The primary reason for withdrawal will be recorded in the eCRF and any data collected up until the point of withdrawal will be used in the data analyses.

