During the trial the vial strength used when dosing will be changed for most subjects, however this will depend on the timing of regulatory approval. The 100mg dose of mepolizumab will be reconstituted from a vial of 250mg/vial strength up until such time that the 100mg/vial strength is available at the site. Once the 100mg/vial strength is available at the site, all subjects will be dosed with 100mg mepolizumab reconstituted from the 100mg/vial strength at their next treatment visit and for the remainder of the study. This change of vial strength will be when subjects are transitioned onto the new drug product. Hereafter, the 250mg/vial strength will be referred to as mepolizumab drug product 1 (MDP1) and the 100mg/vial strength (to which subjects will transition) will be referred to as mepolizumab drug product 2 (MDP2). In the case that MDP2 is not approved for use by ethics/regulatory at a local site/country subjects will continue to be dosed with MDP1.

Subjects will remain on standard of care asthma therapy, which may be adjusted during the study, at the discretion of their physician. The use of Xolair (omalizumab) or any other monoclonal antibody will not be permitted during the course of the study.

Subjects will be monitored in the clinic approximately every 4 weeks to assess adverse events and asthma status. The Asthma Control Questionnaire-5 (ACQ) will be used to assist the investigator in assessing the subject's asthma status along with spirometry at regular intervals. Exacerbations will also be reviewed at each clinic visit. As some subjects may have previously received placebo while participating in the MEA112997 trial and are naive to mepolizumab, safety lab monitoring will be more frequent at the start of the study. Appropriate safety labs will be drawn prior to starting treatment and then at week 4, 8, 12, 24, 36 and 48. Thereafter, these will be collected every 24 weeks. Labs will also be obtained at 12 weeks after discontinuing mepolizumab. Subjects

discontinuing mepolizumab treatment should be monitored for exacerbation of their asthma.

Serum samples for anti-mepolizumab antibody measurements will be obtained from all subjects at Weeks 0, 4, 24 and 48 of the initial year, week 24 and 48 for every additional year, as well as at the Follow-up Visit. Any anti-mepolizumab antibody positive sample will be tested for neutralising antibody.

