**Figure 1 Presentation of Data According to Subject's Former Treatment**

- 2) Change in drug product: Adverse events, immunogenicity and blood eosinophil data will be compared before and after the change in drug product of mepolizumab to investigate whether there is a difference on the safety or efficacy profile following the transition to the new drug product (See [Figure 2](#)).

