### 8.3. Examination of Subgroups

Tabulations of adverse events, immunogenicity and blood eosinophil data will also be reproduced by drug product administered in order to investigate whether there is a differential effect of the two drug products used within the trial (See Section 12 and Section 11.5).

The annualised rate of exacerbations will also be estimated according to blood eosinophil level of  $\geq 150/\mu\text{L}$  or  $< 150/\mu\text{L}$  at baseline within MEA115666.

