### 9.3.2. On-Treatment Phase

The on-treatment phase for any purpose except the classification of exacerbations is defined as being from the day of the first administration to the day of the last administration of study treatment + another 28 days inclusive (but no greater than the data collection cut-off date).

i.e. time on-treatment will otherwise be defined as follows:

For all subjects:

(Date of last administration) – (Date of first administration) + 29  
but no greater than the data collection cut-off date.

This on-treatment phase will be divided into two periods partitioned at the date and time of receiving the new drug product. This transition will occur when a subject switches from dosing with MDP1 to be dosed with MDP2 for the remainder of the study.

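### The by-product adverse-event tables (SAP Tables 7.23-7.26) mix any vial effect with time on treatment and selection, and no listed table gives an AE rate by time since first dose

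*SAP*

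**What the plan says.** The comments refer to SAP Amendment 1.

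- **Purpose.** SAP Section 7, comparison 2: "Adverse events, immunogenicity and blood eosinophil data will be compared before and after the change in drug product of mepolizumab". The stated aim is to see whether the safety or efficacy profile differs after the transition. Section 8.3 says the by-product tabulations are made "in order to investigate whether there is a differential effect of the two drug products used within the trial".
- **Method.** Section 9.5 assigns AEs to products by onset: "the onset date and time of each event will be used to deem in which drug product period the event occurred". Section 9.5.1 defines the rate: "The number of events per 1000 subject-years of exposure will be calculated as" 1000 times the number of AEs, divided by exposure in days over 365.25. Section 12.2 gives the reason: "Exposure adjusted rates of AEs will be presented by drug product to account for any differences in the length of exposure".
- **Outputs.** Tables 7.23 and 7.24 (AEs) and 7.25 and 7.26 (SAEs) give counts and exposure-adjusted rates by product in the As Treated (AT) population. The text and titles mention no time interval and no restriction to subjects who received both products.
- **Order of products.** Section 9.3.2: "This transition will occur when a subject switches from dosing with MDP1 to be dosed with MDP2 for the remainder of the study". Section 3: "In the case that MDP2 is not approved for use by ethics/regulatory at a local site/country subjects will continue to be dosed with MDP1".
- **Withdrawal.** Protocol Section 4.5: "Reasons for withdrawal can include: an adverse event". Protocol Section 3.2 also calls for an investigator review of risk and benefit at least yearly. It takes in treatment-related AEs, and subjects with an unfavourable balance should be withdrawn.

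**The concern.** For anyone who switches, MDP2 time is always later time. Subjects who leave before the switch, and subjects at sites that never receive MDP2, supply MDP1 time only. A rate per subject-year adjusts for how much exposure there is, but not for when it falls or who supplies it.

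The documents make a time pattern plausible without giving its size. Protocol Section 5.2 sets one hour of observation after each of the first three doses and then leaves monitoring to local policy. Laboratory tests are more frequent in the first year (Protocol Tables 2 and 3), and Protocol Section 6.3.4 has clinically significant laboratory abnormalities recorded as AEs. Early time may therefore be observed more closely than later time.

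Two things are at stake. First, a reader may take a difference between the product columns, or the lack of one, as evidence about the vial. Second, the primary objective is to describe long-term safety, yet no listed table appears to show whether AE rates rise, fall or stay level with longer treatment. The nearest outputs are Table 7.22 (first 6 months only, by former treatment) and the profiles of AEs of special interest (AESIs), Tables 7.68-7.76. Section 12.3 describes those profiles as including time to onset, without stating a rate by interval.

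**Working it through.** The documents give no AE time pattern, withdrawal rate or switch date, so there is no planned figure to reproduce. Everything from step 2 on uses assumed inputs and no vial effect.

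**1. The plan's own denominators.** From SAP Sections 9.3.2 to 9.3.2.2, take the first dose on day 0, the switch on day 84 and the last dose on day 364. MDP1 = 84 + 1 = 85 days. MDP2 = (364 - 84) + 28 = 308. Total = 364 + 29 = 393 = 85 + 308. Two longer cases also agree (169 + 560 = 729; 337 + 1092 = 1429). The person-time is consistent; the issue is its timing and source.

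**2. Time pattern only.** Let the AE rate in the first 0.5 year be m times the later rate, and MDP1 last L years. Then MDP2:MDP1 = L / (0.5m + L - 0.5). For m = 1.5 and L = 1, this is 1 / (0.75 + 0.5) = 0.80.

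| m | L = 0.5 | L = 1 | L = 1.5 |
|---|---|---|---|
| 0.75 | 1.33 | 1.14 | 1.09 |
| 1 | 1.00 | 1.00 | 1.00 |
| 1.25 | 0.80 | 0.89 | 0.92 |
| 1.5 | 0.67 | 0.80 | 0.86 |
| 2 | 0.50 | 0.67 | 0.75 |

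**3. AE-related withdrawal only.** Subjects differ in AE rate (gamma, mean 1, variance theta). A share p of AEs leads to withdrawal, the mean rate is lambda per year, the switch is at 1 year and follow-up ends at 3.5 years. The share remaining is S(t) = (1 + theta·p·lambda·t)^(-1/theta), and the rate among those remaining is lambda / (1 + theta·p·lambda·t).

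- lambda 1, theta 0.25 or 1, p 2% or 4%: 7-13% leave because of AEs; ratio 0.99 to 0.94.
- lambda 3, theta 1, p 4%: S(3.5) = 1/1.42, so 30% leave; ratio 0.84. With theta 0.25, 33% leave and the ratio is 0.95.
- lambda 6, theta 1, p 4%: 46% leave; ratio 0.74.

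A simpler model (20% of subjects with 2-3 times the AE rate; 30-50% of them and 5% of the others gone before a week-48 switch) gives 0.98 to 0.93.

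**4. Does splitting by interval help?** Let all subjects switch, at times spread evenly over 0.5 to 1.5 years, with 3.5 years in all. For m = 1.25 / 1.5 / 2, the all-exposure ratios are 0.89 / 0.80 / 0.67. Within weeks 24-48 they are 0.97 / 0.95 / 0.90, and within weeks 48-96 they are 1.00. For m = 0.75, 1.14 becomes 1.03 and 1.00. The remainder in weeks 24-48 arises because the assumed 6-month effect runs about 2 weeks past week 24. A withdrawal ratio of 0.94 (12% leaving) becomes 0.99-1.00, and 0.75 (46% leaving) becomes 0.94-0.98.

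**5. Where splitting by interval fails.** Let 20% of subjects be at sites that never switch, with an AE rate 1.5 times that of the others. All-exposure MDP1 rate: (0.8 × 1 × 1 + 0.2 × 3.5 × 1.5) / (0.8 × 1 + 0.2 × 3.5) = 1.85 / 1.5 = 1.23; ratio 0.81. From week 96 all MDP1 time is theirs, and the ratio is 1/1.5 = 0.67, further from 1. With an AE rate 0.67 times the others', 1.18 becomes 1.49. These sites must therefore be kept apart. At switching sites no MDP1 time then remains after about week 78 (1.5 years).

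**6. Precision.** Assume 300 subjects in a 24-week interval, half per product: 150 × 168/365.25 = 69 subject-years each. The 95% factor either way is exp(1.96·sqrt(1/e1 + 1/e2)), where e1 and e2 are the event counts.

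- AEs at 3 per year: 207 per product, factor 1.21. With 1.38 AEs per subject and between-subject variance 0.25-1, the factor widens to 1.25-1.35.
- SAEs at 0.1-0.2 per year: 7-14 per product, factor 2.9-2.1. For 200-600 subjects (protocol cap 608): 5-28 SAEs, factor 3.6-1.7.
- Equal 24-week windows in 200-400 switchers: 9-37 SAEs per window, factor 2.5-1.6.

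**The case against.** The strongest reply is that nothing in the plan is contradicted. Section 12.2 claims an adjustment for length of exposure, and the rate delivers that. There is no hypothesis, ratio or test (SAP Sections 2.3 and 7). This stands: the point limits interpretation and does not show an invalid analysis.

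Second, no real time pattern or withdrawal rate is known, and constant rates with AE-unrelated withdrawal give 1.00. This also stands. A reader might infer that a difference between products is as likely to come from time or selection as from the vial. The documents do not support that, because they give nothing from which to weigh the explanations.

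Third, the product question does not rest on Tables 7.23-7.26 alone. Eosinophils have a pre/post-change table limited to subjects sampled in both periods (Table 6.10), and anti-drug and neutralising antibodies have Tables 7.56 and 7.57. This is correct, but AEs, the primary endpoint, have no counterpart.

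Fourth, the display shells and the Program Safety Analysis Plan are separate documents. A reader might infer that the AESI profiles hold nothing beyond time to onset, or that Tables 7.24 and 7.26 lack a total column. Neither follows: Section 12.3 leaves the profile contents open, and an overall rate can be derived.

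Fifth, an unrestricted product-by-interval split can mislead more than the planned tables (step 5) and is sparse for SAEs. This stands and limits the fix. If switch dates fall close together, few intervals will contain both products.

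Finally, no objective names a trend in AE rate. True, but rates over time are a natural part of describing a long-term safety profile.

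**Conclusion.** The concern holds in a limited form. Tables 7.23-7.26 cannot by themselves serve the purpose in SAP Sections 7 and 8.3, because product is tied to time on treatment and to who remained or could switch. Separately, judged by titles and text, no listed table gives an AE rate by time since first dose.

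The size and direction of any bias are unknown. In the assumed cases a time pattern moves the ratio to between 0.50 and 1.33, whereas AE-related withdrawal of 7-13% moves it only to 0.94-0.99. These figures show what could happen and do not estimate what will. A reader might conclude that the comparison will be biased, or biased towards fewer events on MDP2; the documents support neither. This is a cheap improvement to a descriptive analysis.

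**What to change.** 1. Add Section 9.5.1 rates for AEs and SAEs by interval since first dose (first 24 weeks, weeks 24-48, then 48-week intervals) for the whole AT population, using subject-time at risk in each interval.
2. For the product comparison of all AEs, show rates by product only within intervals where both products are in use at sites that switched. Table 5.09 (visit of switch) and Listing 7.01 (product at each dose) identify these. Show never-switching sites separately. Do not extend the split to later intervals or to AESIs, and treat any SAE split as descriptive only.
3. Optionally, add a table in subjects treated with both products, over equal windows (for example 24 weeks) either side of the first MDP2 dose and outside the initial months. State its limits: events leading to death or withdrawal before the switch are excluded by construction, season or calendar time may differ between windows, and precision is low.
4. State in Section 12.2 that the all-exposure product split does not isolate a vial effect.

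Cost: SAP wording and a few descriptive tables from data already collected. The downside is sparse later intervals and low precision: about 5-28 SAEs per product per 24-week interval under the assumptions above, and wider intervals for AEs if events cluster within subjects.
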